11.1.2 Adverse Event of Special Interest

AESIs (serious or non-serious) are a subset of Events to Monitor (EtMs) of scientific and medical concern specific to the IMP or to the Sponsor's product or research, for which ongoing monitoring and rapid communication by the Investigator to the Sponsor is required. Such an event might require further investigation in order to characterize and understand it. Depending on the nature of the event, rapid communication by the trial Sponsor to other parties (e.g., MAH, Regulatory Authorities) may also be warranted.

Adverse events of special interest (AESI) (synonym: Events of Clinical Interest (ECI)) either serious or non-serious, are required to be reported by the investigator to the Sponsor/ZKS in the SAE form immediately (i.e., no more than 24 hours after learning of the event) and will be recorded on the AE page of the eCRF additionally. Adverse events of special interest for this study include the following:

Table 3: Adverse Event of Special Interest

Adverse Events of Special Interest
An elevated AST or ALT lab value that is greater than or equal to 3X the upper limit of normal and an elevated total bilirubin lab value that is greater than or equal to 2X the upper limit of normal and, at the same time, an alkaline phosphatase lab value that is less than 2X the upper limit of normal, as determined by way of protocol-specified laboratory testing or unscheduled laboratory testing.*

*Note: These criteria are based upon available regulatory guidance documents. The purpose of the criteria is to specify a threshold of abnormal hepatic tests that may require an additional evaluation for an underlying etiology.

AESIs (ECI) must be reported within 1 working day after becoming aware by the Sponsor to MSD Pharmacovigilance Germany [REDACTED] [REDACTED] [REDACTED] [REDACTED] [REDACTED] [REDACTED]

For the time period beginning when the consent form is signed until treatment allocation, any AESI (ECI), or follow up to an AESI (ECI), that occurs to any participant must be reported within 1 working day after becoming aware by the Sponsor to MSD Pharmacovigilance Germany if it causes the participant to be excluded from the trial, or is the result of a protocol-specified intervention, including but not limited to washout or discontinuation of usual therapy, diet, placebo treatment or a procedure.

For the time period beginning at treatment allocation through 110 days following cessation of treatment, or 30 days following cessation of treatment if the participant initiates new anticancer therapy, whichever is earlier, any AESI (ECI), or follow up to an AESI (ECI), whether or not related to MSD product, must be reported within 1 working day after becoming aware by the Sponsor to MSD Pharmacovigilance Germany

11.1.3 Adverse Drug Reaction

An adverse drug reaction (ADR) is any noxious and unintended response to a medicinal product related to any dose. The phrase "responses to a medicinal product" means that a causal relationship between a medicinal product and an adverse event is at least a reasonable possibility. An ADR should be recorded on the AE page of the eCRF.

11.1.4 Special Situations

Uses of the IMP outside what is foreseen in the protocol and defined below as „special situations“ are subject to the same obligation to report as adverse reactions. All special

situations, even in absence of an AE, that occur during the defined study period must be recorded on the source documentation, transcribed into the eCRF and in addition reported to the Sponsor/ZKS on the „Report form for SAEs, AESIs and Special Situations“.

Note: All instances of incorrect medication not in accordance with the study protocol should be additionally categorized as deviation in the eCRF.

- **Pregnancy/Breast feeding**

see section 11.5

- **Overdose***

Any administration of a quantity of a medicinal product given per administration or cumulatively that results in drug exposure exceeding that which is defined in the protocol.

- **Abuse**

Intentional, non-therapeutic use of a drug product or substance, even once, to achieve a desired psychological or physiological effect. Therefore, abuse potential refers to the likelihood that abuse will occur with a particular drug product or substance with CNS activity. Desired psychological effects can include euphoria, hallucinations and other perceptual distortions, alterations in cognition, and changes in mood.

- **Misuse**

Any intentional therapeutic use of a drug product in an inappropriate way. Inappropriate use should be considered in the context of the clinical trial protocol.

- **Medication Error**

An unintended failure in the drug treatment process.

Examples include administration of a drug product in the wrong dose, by an incorrect route, or to the wrong person; administration of a drug product resulting in a drug interaction due to drugs or foods that are known to interact; administration of the wrong drug product; or inadvertently consuming a greater than prescribed dose of a drug product (e.g. double dose) due to memory lapse. Therapeutic errors may be made by the patient, physician, pharmacist, clinical study staff etc.

- **Occupational exposure**

Exposure to an IMP, as a result of one's professional or non-professional occupation.

- **Lack of therapeutic efficacy**

Although MZL is a serious and life-threatening disease, patients will receive approved therapies while participating in this study. Efficacy of Rituximab/Pembrolizumab combination treatment has yet to be demonstrated in the MZL population. Therefore, lack of therapeutic efficacy is not the scope of this study.

*an overdose of MSD product, as defined in Section 11.3.

11.2 Evaluation of Adverse Events

A qualified Investigator will evaluate all adverse events as to:

11.2.1 Seriousness

A serious adverse event (SAE) is any AE occurring at any dose that results in any of the following outcomes or actions:

- Results in death;
- Is life-threatening (i.e., in the opinion of the Investigator, the subject is at immediate risk of death from the AE); it does not refer to an event which hypothetically might have caused death if it were more severe
- Requires inpatient hospitalization or prolongation of existing hospitalization (hospitalization is defined as an inpatient admission, regardless of length of stay);
- Results in persistent or significant disability/incapacity (a substantial disruption of the subject's ability to conduct normal life functions);
- Is a congenital anomaly/birth defect;
- Any other event that the Investigator judges to be an important medical event
- adverse event associated with an overdose of IMP

Important medical events are defined as those occurrences that may not be immediately life threatening or result in death, hospitalization, or disability, but may jeopardize the subject or require medical or surgical intervention to prevent one of the other outcomes listed above. Medical and scientific judgment should be exercised in deciding whether such an AE should be considered serious. Suspected transmission of an infectious agent by a medicinal product will be reported as a serious adverse event.

If an AE is considered serious, both the AE page/screen of the eCRF and the SAE Report Form must be completed.

For each SAE, the Investigator will provide at least information on severity, start and stop dates, relationship to IMP, action taken regarding IMP, and outcome.

Events excluded from SAE reporting are hospitalizations for:

- A standard procedure for protocol therapy administration. However, hospitalization or prolonged hospitalization for a complication of therapy administration will be reported as an SAE.
- Routine treatment or monitoring of the studied indication not associated with any deterioration in condition.

- The administration of blood or platelet transfusion as routine treatment of studied indication. However, hospitalization or prolonged hospitalization for a complication of such transfusion remains a reportable SAE.
- A procedure for protocol/disease-related investigations (e.g., surgery, scans, endoscopy, sampling for laboratory tests, bone marrow sampling). However, hospitalization or prolonged hospitalization for a complication of such procedures remains a reportable SAE.
- A procedure or hospitalization for progression/relapse investigations (e.g., surgery, scans, endoscopy, sampling for laboratory tests, bone marrow sampling).
- Hospitalization or prolongation of hospitalization for technical, practical, or social reasons, in absence of an AE.
- A procedure that is planned (i.e., planned prior to signing informed consent); must be documented in the source document and the eCRF. Hospitalization or prolonged hospitalization for a complication remains a reportable SAE.
- Emergency outpatient treatment or observation that does not result in admission, unless fulfilling other seriousness criteria above.
- Sign, symptoms and physical findings indicative of progression of lymphoma are not to be reported as “Serious Adverse Event”.
- “Alopecia” toxicity (any grade) will never be reported as “Serious Adverse Event”.
- Serious adverse events will not be recorded 30 days after the start of a new chemotherapy treatment, with the exception of second primary malignancies or if it is related to the study drug as assessed by the investigator.

11.2.2 Severity / Intensity

For both AEs and SAEs, the Investigator must assess the severity / intensity of the event.

The severity / intensity of AEs will be graded based upon the subject’s symptoms according to the current active minor version of National Cancer Institute (NCI) Common Terminology Criteria for Adverse Events (CTCAE, Version 5.0):

AEs that are not defined in the NCI CTCAE (v 5.0) should be evaluated for severity / intensity according to the following scale:

- *Grade 1 = Mild – transient or mild discomfort; no limitation in activity; no medical intervention/therapy required*
- *Grade 2 = Moderate – mild to moderate limitation in activity, some assistance may be needed; no or minimal medical intervention/therapy required*

- *Grade 3 = Severe – marked limitation in activity, some assistance usually required; medical intervention/therapy required, hospitalization is possible*
- *Grade 4 = Life threatening – extreme limitation in activity, significant assistance required; significant medical intervention/therapy required, hospitalization or hospice care probable*
- *Grade 5 = Death - the event results in death*

Specific NCI Working Group or other criteria pertinent to the indication may also be used as applicable.

The term “severe” is often used to describe the intensity of a specific event (as in mild, moderate or severe myocardial infarction); the event itself, however, may be of relatively minor medical significance (such as severe headache). This criterion is *not* the same as “serious” which is based on subject/event *outcome* or *action* criteria associated with events that pose a threat to a subject’s life or functioning.

Seriousness, not severity, serves as a guide for defining regulatory obligations.

11.2.3 Causality

The Investigator must determine the relationship between the administration of the IMPs and the occurrence of an AE/SAE as Not Related or Related as defined below:

Not related: **A** causal relationship is **unlikely or remote** between the adverse event and study drug administration and other medications, therapeutic interventions, or underlying conditions provide a sufficient explanation for the observed event

Related: **A** causal relationship is **possible** between the adverse event and study drug administration and other medications, therapeutic interventions, or underlying conditions do not provide a sufficient explanation for the observed event

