8.3 Dose adjustments

In general, the following rules should be adhered to:

- In case of several toxicities, the most severe reaction is to be taken for dose reductions.
- Patients must have at least a hemoglobin value ≥ 7.5 g/dL, an ANC $\geq 0.5 \times 10^9/L$, **and** a platelet count $\geq 30 \times 10^9/L$ before continuing treatment.
- Delays of cycles will be done by regimen and not by individual compound.
- Dose reductions will be done by individual compounds as described below.
- If there is the necessity to stop application of single compounds, treatment can be continued omitting the individual drug with the other compounds of the regimen.
- If there is a delay in treatment of > 3 weeks, contact the 'Clinical trials office (Ulm)'.

8.3.1 Pembrolizumab i.v.

8.3.1.1 *Dose Modification and toxicity management for irAEs associated with Pembrolizumab and combination therapy*

AEs associated with Pembrolizumab exposure, including coadministration with additional compounds, may represent an immunologic etiology. These immune-related AEs (irAEs) may occur shortly after the first dose or several months after the last dose of Pembrolizumab/ combination treatment and may affect more than one body system simultaneously. Therefore, early recognition and initiation of treatment is critical to reduce complications. Based on existing clinical study data, most irAEs were reversible and could be managed with interruptions of Pembrolizumab/ combination treatment, administration of corticosteroids and/or other supportive care. For suspected irAEs, ensure adequate evaluation to confirm etiology or exclude other causes. Additional procedures or tests such as bronchoscopy, endoscopy, skin biopsy may be included as part of the evaluation. Based on the severity of irAEs, withhold or permanently discontinue Pembrolizumab and administer corticosteroids.

Dose modification and toxicity management guidelines for irAEs associated with Pembrolizumab/ combination treatment are provided in Table 1.

Attribution of Toxicity:

When study interventions are administered in combination, attribution of an adverse event to a single component is likely to be difficult. Therefore, while the investigator may attribute a toxicity event to the combination, to rituximab alone or to pembrolizumab alone, for adverse events listed in Table 1, both interventions must be held according to the criteria in Table 1.

Holding Study Interventions:

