11.6 Reporting of Serious Adverse Events

11.6.1 Reporting period

All events that meet one or more criteria of seriousness that occurred **from the time the patient's signed informed consent up to 110 days after the last study drug administration**, regardless the relationship to the study treatment requires the completion of an SAE Report Form in addition to being recorded on the AE page of the eCRF.

A Serious Adverse Event that occurs after this time, including during the follow-up period, **if considered related to the study medication**, will be reported regardless of the time between the last drug administration and the event onset.

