7.6 Variables for Safety Analysis

Safety evaluations include AEs/SAEs/AESIs, clinical laboratory parameters (hematology, serum chemistry, serum immunoglobulin (IgG, IgM, IgA), CRP), and ECG. Laboratory parameters cover parameters of serum chemistry, hematology, quantitative immunoglobulins (IgA, IgG, IgM), and CRP. More details are in the parts 7.1 and 7.2, see above. For ECG, the frequencies of 'Normal or not clinically significant' or 'Clinically significant' will be calculated.

The severity of AEs will be graded using the NCI-CTCAE version 5.0 dictionary. An AE is defined as any event arising or worsening after start of study drug administration until 110 days (based on five times the half-life of Rituximab and Pembrolizumab) after the last study drug intake. All AEs, drug related AEs, serious AEs will be summarized by MedDRA classification (SOC and preferred term) and worst CTCAE grade. Additionally, adverse events of special interest (AESIs) will be analysed as a separate category.

Adverse events (AE), serious adverse events (SAE) adverse events of special interest (AESI): Following variables will be used in the analysis of AEs, SAEs and AESI: *SUBJECTID*, *AESPID*, *AETERM*, *AETOXGR*, *AERELPEM*, *AERELRIT*, *AEACNPEM*, *AEACNRIT*, *AESER*, *AESI*, *AESS*, *AESSCAS*, *AESTDAT*, *AEOUT*, and *AEENDAT* in table *AE*. For the analysis of AEs, the final outcome will be analysed only. AEs, SAEs (variable *AESER* in table *AE*) and AESIs (variable *AESI* in table *AE*) will be analysed separately. Additionally, AEs / SAEs / AESIs of grade ≥ 3 (variable *AETOXGR* in table *AE*) will be analysed separately.

Concomitant medication: Concomitant medication is documented during treatment period. Variables for analysis are *SUBJECTID*, *CMSPID*, *CMTRT*, *CMINDC*, *CMDSTXT*, *CMFREQ*, *CMROUTE*, *CMROUTEOTH*, *CMSTDAT*, *CMONGO*, and *CMENDAT* in table *CM*.

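### Protocol 11.2.3 defines Related more narrowly than the ADR definition in 11.1.3 and leaves two of four combinations without a category, so drug-related events can be misclassified

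*Protocol*

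**What the plan says.** Protocol 11.2.3 puts the rating on the local physician, who "must determine the relationship between the administration of the IMPs and the occurrence of an AE/SAE as Not Related or Related as defined below". There is no third category.

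Each category joins two conditions with an *and*:

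- Related: the event has a possible causal link with "study drug administration and other medications, therapeutic interventions, or underlying conditions do not provide a sufficient explanation for the observed event".
- Not related: a causal link is unlikely or remote, and "other medications, therapeutic interventions, or underlying conditions provide a sufficient explanation for the observed event".

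Protocol 11.1.3 uses a different test. An event is an adverse drug reaction (ADR) when "a causal relationship between a medicinal product and an adverse event is at least a reasonable possibility". Nothing is said there about alternative explanations.

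The rating is then used in four places:

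- Protocol 11.6.4: expedited reporting covers SAEs that are unexpected and suspected to be related.
- Protocol 11.6.1: after the 110-day window an SAE is reportable only if considered related; such an SAE "will be reported regardless of the time between the last drug administration and the event onset".
- Protocol 11.2.1: from 30 days after the start of a new chemotherapy, SAEs are recorded only if they are second primary malignancies or related.
- SAP 7.6: "All AEs, drug related AEs, serious AEs will be summarized by MedDRA classification (SOC and preferred term) and worst CTCAE grade".

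SAP 7.6 lists relationship to pembrolizumab (AERELPEM) and to rituximab (AERELRIT) as separate variables. It does not say how the two combine into a drug-related AE.

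**The concern.** Two sections of one protocol give different tests for the same judgement, and the stricter one drives reporting and analysis. The events on which they differ are those that the drugs may have caused but that something else could also explain. The protocol gives reason to expect some in this trial. It describes patients who are mostly elderly, often with comorbidity (4.3), cytopenias that may come from the disease (7.1, 8.3.2), and frequent infections under rituximab (8.1.3.4).

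Toxicity of the combination is part of the stated objective (Synopsis; SAP 2.1), so the drug-related AE summary is a result that readers will use. Late events add to the concern. Protocol 8.3.1.1 warns that immune-related events may appear several months after the last dose. SAP 2.1 puts the end-of-treatment visit of the last enrolled patient at 06 Dec 2024. Counting 110 days from that visit gives 26 March 2025, so this patient's window closed by then at the latest. From that point the relatedness rating decides whether an SAE other than a secondary malignancy is reported at all.

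**Working it through.** The documents give no figure on this point, so there is none to reproduce. The check is a cross-tabulation of the two conditions in 11.2.3, set beside 11.1.3.

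| Causal link | Sufficient alternative explanation? | Category under 11.2.3 | ADR under 11.1.3? |
|---|---|---|---|
| Possible | No | Related | Yes |
| Possible | Yes | none | Yes |
| Unlikely or remote | No | none | No |
| Unlikely or remote | Yes | Not related | No |

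1. **Coverage.** Two of the four rows have no category, although a rating is compulsory.
2. **Consistency.** Related is row 1 only; an ADR is rows 1 and 2. Related is therefore a strict subset of ADR, and every row 2 event is an ADR that cannot be rated Related on a literal reading.
3. **Direction.** A row 2 event rated Not related lowers the related count. A row 3 event rated Related raises it. The text does not say where either goes.
4. **Size.** Let *s* be the share of reasonably possible events that also have a sufficient alternative, and *q* the share of those that sites rate Not related. The fraction of ADRs lost from Related is *s* × *q*. The documents give neither value, so these are assumptions:

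| *s* | *q* = 0 | *q* = 0.5 | *q* = 1 |
|---|---|---|---|
| 0.1 | 0% | 5% | 10% |
| 0.3 | 0% | 15% | 30% |
| 0.5 | 0% | 25% | 50% |

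The loss is zero if investigators ignore the second condition. The range shows that the wording alone does not fix the size.

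5. **What depends on the rating.** The exposed outputs are the drug-related AE summary, SUSAR classification, non-malignancy SAEs after 110 days, and SAEs from 30 days after new chemotherapy. SAEs up to 110 days are otherwise reported whatever the relationship (11.6.1). The listings and proportions in SAP 8.2.6 are all-causality.

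**The case against.** The strongest objection is that under-counting does not follow from the text. A possible event with a sufficient alternative fails Related, but it also fails Not related, because its link is not unlikely or remote. An investigator who treats possible versus unlikely as the deciding question would rate it Related, and 11.1.3 supports that choice. The row with an unlikely link and no alternative could push the count up. This stands: a reader might infer that drug-related events *are* under-counted, and the documents show only that they *can* be.

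A second tempting inference is that each study drug could serve as the other's alternative explanation, so that an event is related to neither. The text does not support this. Section 11.2.3 speaks of the IMPs together and sets study drug administration against other medications. Section 8.3.1.1 concedes that "attribution of an adverse event to a single component is likely to be difficult" but expressly allows attribution to the combination.

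A third is to turn the infection or infusion-reaction frequencies in 8.1.3 into a number of misrated patients. Those figures count events. They do not count events that combine a possible drug cause with a sufficient alternative.

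There are also safeguards. A missing SAE causality is treated as related (11.6.2), and malignancies are reported throughout follow-up (11.4, 11.6.2). These narrow the problem. The first does not help once a site has entered Not related, and the SAP has no such default for non-serious AEs (missing values form a separate category under SAP 8.1).

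Finally, treatment has ended, so new wording cannot by itself change ratings already made, and re-querying only Not related events would bias the correction upwards. Both points are fair, and they shape the remedy.

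**Conclusion.** The definition is wrong as written: it contradicts 11.1.3 and leaves two of four combinations without a category while demanding a rating. Drug-related AEs, SUSARs, non-malignancy SAEs after 110 days and SAEs from 30 days after new chemotherapy can be misclassified.

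Under-counting is the more plausible direction. This is a judgement: it assumes that some sites apply the second condition literally, and that possible events with another explanation outnumber unlikely events with none in this population. The size is unknown and no percentage should be attached to it. All-causality AE and SAE counts, and SAE reporting up to 110 days, do not depend on the rating. The correction should be made, but the overall safety picture does not hang on it.

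**What to change.** - **Protocol 11.2.3:** reword to match 11.1.3. Related: at least a reasonable possibility that pembrolizumab, rituximab or both caused the event, whether or not another explanation exists. Not related: no reasonable possibility. Apply this to events still reportable in follow-up.
- **SAP 7.6:** define a drug-related AE as one related to pembrolizumab OR rituximab.
- **Data:** if the database is still open, ask sites to re-confirm relationship under the aligned definition for all SAEs and all grade 3 or higher events, whatever rating they now carry. Querying both ratings covers both unclassified combinations.

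The cost is one protocol amendment, which needs ethics committee and authority approval under Protocol 16.9, one sentence in the SAP, and a small query round in 22 patients. The drug-related AE rate may become slightly less favourable.
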